Appendix 3**Criteria for Identifying ECG Measurements of Potential Clinical Relevance**

Variable	Criterion Value ^a	Change Relative to Baseline ^a
Rhythm		
Sinus tachycardia ^b	≥ 110 bpm	increase of ≥ 15 bpm
Sinus bradycardia ^c	≤ 60 bpm	decrease of ≥ 15 bpm
Supraventricular premature beat	all	not present \rightarrow present
Ventricular premature beat	all	not present \rightarrow present
Supraventricular tachycardia	all	not present \rightarrow present
Ventricular tachycardia	all	not present \rightarrow present
Atrial fibrillation	all	not present \rightarrow present
Atrial flutter	all	not present \rightarrow present
Conduction		
1 atrioventricular block	$PR \geq 200$ msec	increase of ≥ 50 msec
2 atrioventricular block	all	not present \rightarrow present
3 atrioventricular block	all	not present \rightarrow present
Left bundle-branch block	all	not present \rightarrow present
Right bundle-branch block	all	not present \rightarrow present
Pre-excitation syndrome	all	not present \rightarrow present
Other intraventricular conduction block ^d	$QRS \geq 120$ msec	increase of ≥ 20 msec
Infarction		
Acute or subacute	all	not present \rightarrow present
Old	all	not present \rightarrow present
		≥ 12 weeks post trial entry
ST/T Morphological		
Myocardial ischemia	all	not present \rightarrow present
Symmetrical T-wave inversion	all	not present \rightarrow present
Increase in QTc		
< 12 years old	$QTcF \geq 450$ msec	increase of 60 msec
≥ 12 years old	$QTcF \geq 460$ msec	from baseline

QTc = corrected QT interval.

^aThe criterion value and change relative to baseline represented in this table are intended to identify on-treatment values outside of normal changes and that could potentially be clinically relevant. In order to be identified as potentially clinically relevant, the on-treatment value must meet the “Criterion Value” and also represent a change from the subject’s baseline value of at least the magnitude shown in the “Change Relative to Baseline” column. When evaluating these values, the emotional state of the subject must be taken into consideration (eg, crying, screaming) and documented as applicable.

^bNo current diagnosis of supraventricular tachycardia, ventricular tachycardia, atrial fibrillation, atrial flutter, or other rhythm abnormality.

^cNo current diagnosis of atrial fibrillation, atrial flutter, or other rhythm abnormality.

^dNo current diagnosis of left bundle branch block or right bundle branch block.

Protocol 405-201-00037

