8.7.4 Electrocardiogram

Electrocardiograms will be performed at the time points described in the schedule of assessments ([Table 1.3-1](#)). Subjects should be monitored for potentially clinically significant ECG results ([Section 10.7](#)). Any abnormalities considered by the investigator to be clinically significant are to be recorded as AEs on the AE eCRF.

The 12-lead ECGs will be performed in the supine position. Predose 12-lead ECGs conducted at check-in (Day -1 or Day 1) will be performed in triplicate, taken at least 1 minute apart following a 10-minute rest in the supine position. The average of the 3 values will be the baseline value. Based on the QTcF, a subject will be excluded if the correction is ≥ 450 msec for more than 1 of the 3 time points of triplicate predose ECGs performed for subjects < 12 years old or ≥ 460 msec for more than 1 of the 3 time points of triplicate predose ECGs performed for subjects ≥ 12 years old.

A central ECG service will be utilized for reading all ECGs in order to standardize interpretations for the safety analysis. In addition, ECG results will be evaluated at the trial site to monitor safety during the trial.

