10.5 Physical Examination Data

A complete physical examination will be performed at screening, check-in (Day -1 or Day 1), and Day 2/ET. A complete physical examination will consist of measurement of height and weight and an assessment of the following body systems: head, eyes, ears, nose, and throat; thorax; abdomen; extremities; neurological; and skin and mucosae. Any abnormalities considered by the investigator to be clinically significant are to be recorded as AEs on the AE eCRF.

Physical examination data will be presented in a listing.

Protocol 405-201-00037

10.6 **Electrocardiogram (ECG) Data**

Descriptive statistics of change from baseline in heart rate and ECG intervals of PR, QRS, QT, and QTcF, will be provided by time point and mode of administration. The incidence of potentially clinically relevant ECGs, as defined in [Appendix 3](#) will be summarized by time point and mode of administration. ECG data that are potentially clinically relevant will also be listed out by subject.

When ECG assessment is repeated, the last repeat value will be used in the summary for that visit. Unscheduled ECG value will not be summarized in the change from baseline table but will be included in incidence table.

10.7 **Potential Serious Hepatotoxicity**

A listing will be provided to present the incidence of subjects who experience an elevation in AST or ALT that is ≥ 3 times the ULN.

10.8 **Other Safety Data**

The “Baseline/Screening” version of the C-SSRS will be completed at the screening visit and the “Since Last Visit” version of the C-SSRS will be completed at check-in (Day -1 or Day 1) and EoT/ET (Day 2).

The incidence of suicidal behavior and suicidal ideation will be summarized by time point and mode of administration.

Protocol 405-201-00037

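### The ECG table and listing in SAP 10.6 can omit a child who newly crosses the QTcF limit, or whose QTcF rises by 60 msec or more, because Appendix 3 requires both together

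*SAP*

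**What the plan says.** SAP Appendix 3 has two columns for each ECG variable: a criterion value and a change relative to baseline. In the row for increases in QTc, the criterion value is QTcF of at least 450 msec under 12 years and at least 460 msec from 12 years. The change entry is "increase of 60 msec".

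Footnote a joins the columns. It says "In order to be identified as potentially clinically relevant, the on-treatment value must meet the" criterion column and must also differ from the child's "baseline value of at least the magnitude shown in the" change column. Protocol Appendix 7 has the same table and rule.

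SAP 10.6 plans three ECG outputs:

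- Change statistics: "Descriptive statistics of change from baseline in heart rate and ECG intervals of PR, QRS, QT, and QTcF, will be provided by time point" and by mode of administration.
- An incidence table of potentially clinically relevant ECGs, defined by Appendix 3.
- A listing on the same definition: "ECG data that are potentially clinically relevant will also be listed out by subject".

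On unscheduled recordings it says: "Unscheduled ECG value will not be summarized in the change from baseline table but will be included in incidence table".

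Protocol 8.7.4 defines baseline as the mean of the triplicate predose ECGs. It excludes a child who is at or above the same limits "for more than 1 of the 3 time points of triplicate predose ECGs performed for subjects" in the relevant age group, as does exclusion criterion 14 in Protocol 5.2.2. It also says: "Any abnormalities considered by the investigator to be clinically significant are to be recorded as AEs on the AE eCRF".

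**The concern.** A joint rule is narrower than either of its parts. It leaves out two kinds of child: one whose QTcF newly passes the limit with a rise of less than 60 msec, and one whose QTcF rises by 60 msec or more but stays under the limit. Before dosing, the same 450/460 msec limits count without any change condition. After dosing, a child under 12 with a baseline of 449 msec must reach 509 msec to be flagged.

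The other planned outputs do not close the gap. Section 10.6 summarises only change in QTcF, not the observed value; SAP 10.3, by contrast, summarises both for laboratory tests. Section 10.6 plans no full ECG listing. Unscheduled ECGs, some of which may be taken because of a concern, are kept out of the change statistics and can show up only through the flag. Recording an AE depends on the investigator's judgement and not on the plan's cut-offs.

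What is at stake is the reading of the safety table. A count of zero would be taken to mean that no child passed the plan's QTc cut-offs, when it means only that no child passed both at once.

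**Working it through.** The plan gives no figure on this point to reproduce, so the check applies the rule directly.

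**Inputs**

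- Limit L: 450 msec under 12 years, 460 msec from 12 years (SAP Appendix 3; Protocol Appendix 7).
- Change: 60 msec. The table entry carries no inequality sign; footnote a makes it a minimum, so it is read as 60 or more.
- Baseline b: mean of the three predose ECGs (Protocol 8.7.4). The baselines below are illustrative, because the documents give no QTcF distribution.
- Values are in whole msec.

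**Formulas**

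- An on-treatment value v is flagged only if v ≥ L and v − b ≥ 60. The lowest flagged value is max(L, b + 60).
- Unflagged new crossing: L to b + 59, when b < L and b + 60 > L.
- Unflagged rise of 60 msec or more: b + 60 to L − 1, when b + 60 < L.
- The two conditions coincide only at b = L − 60, which is 390 msec under 12 years and 400 msec at 12 years.

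**Results**

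| Age | Baseline | Flagged from | New crossing not flagged | Rise ≥ 60 not flagged |
|---|---|---|---|---|
| < 12 | 380 | 450 | none | 440–449 |
| < 12 | 390 | 450 | none | none |
| < 12 | 400 | 460 | 450–459 | none |
| < 12 | 420 | 480 | 450–479 | none |
| < 12 | 440 | 500 | 450–499 | none |
| < 12 | 449 | 509 | 450–508 | none |
| 12 | 380 | 460 | none | 440–459 |
| 12 | 400 | 460 | none | none |
| 12 | 420 | 480 | 460–479 | none |
| 12 | 440 | 500 | 460–499 | none |
| 12 | 459 | 519 | 460–518 | none |

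**Two examples**

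- Under 12 years, 445 to 500 msec: the rise is 500 − 445 = 55, below 60. The limit is passed by 50 msec, but flagging starts at 445 + 60 = 505. Not flagged.
- 380 to 445 msec: the rise is 445 − 380 = 65, above 60, but 445 is below both 450 and 460. Not flagged at either age.

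**Can these baselines occur?** Yes. Exclusion requires more than one of the three predose readings to be at or above the limit, so baselines just under it are eligible.

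**Exposure.** At most 12 children may be treated. In Protocol Table 1.3-1 the Day 1 ECG is a predose assessment (footnote d), so the only scheduled postdose ECG is at Day 2/EoT/ET. Unscheduled ECGs come on top of that.

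**The case against.** The joint rule is a deliberate and consistent choice. Protocol and SAP agree on it, the vital-sign appendices use the same construction, and it keeps children with stable high baselines from being flagged. The data are not lost. All ECGs are read centrally and also reviewed at the site. If the change statistics include a maximum, a scheduled rise of 60 msec or more would show there. The entry comparison is also not like for like: entry needs more than one of three readings at the limit, whereas the protocol specifies triplicates only before dosing. A count of any postdose value at the limit would pick up a move from 448 to 451 msec, which may be noise. Finally, this is a small, descriptive, single-dose pilot.

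Part of this stands. There is no conflict between the documents, no suggestion that a child would go unreviewed, and the weight is modest. Some extra values would be trivial on medical review.

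The rest does not remove the point. Central reading and site review create no planned output. Section 10.6 does not say which descriptive statistics it will give; a maximum change would show neither the child nor the absolute value, and would not reveal a crossing with a smaller rise. Unscheduled ECGs are outside those statistics altogether. Children with stable high baselines can be kept out by counting only new crossings. Nor is a joint rule universal in the plan: most laboratory criteria act on the value alone, and the orthostatic criteria disregard baseline.

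**Conclusion.** The concern holds. As written, the SAP 10.6 incidence table and listing can show no potentially clinically relevant QTc value although a child has newly crossed the plan's own limit or risen by its own 60 msec.

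The size depends on baseline. The unflagged range of new crossings is 10 msec wide at a baseline of 400 msec under 12 years (450–459), and 59 msec wide at 449 msec under 12 years (450–508) or 459 msec at age 12 (460–518). Unflagged rises of 60 msec or more occur only with baselines below 390 msec (under 12) or 400 msec (age 12). How often a case would be missed cannot be stated without a baseline distribution.

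The conclusion rests on the literal wording of footnote a and on the triplicate mean as baseline. It concerns safety reporting only. It should be corrected because the remedy is cheap and, with so few children, one omitted child matters in a descriptive table.

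**What to change.** Keep the combined flag as it is. In SAP 10.6 add two separate counts, by time point and mode of administration, and one by-subject listing, all including unscheduled ECGs:

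- (a) postdose QTcF of at least 450 msec (under 12 years) or at least 460 msec (from 12 years), not present at baseline, whatever the change;
- (b) an increase in QTcF of at least 60 msec from baseline, whatever the value.

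Name the baseline in the new table as the mean of the triplicate predose ECGs, following Protocol 8.7.4. SAP 10.6 states no ECG baseline and says the last repeat is used, which could be misread as applying to the triplicate. The choice matters: predose readings of 440, 445 and 455 msec have a mean of 446.7 msec (1340 / 3), below the 450 msec limit although one reading is above it.

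The cost is one table and one listing from data already collected, using cut-offs already in the plan, and a few more values for medical review. The criteria in Protocol Appendix 7 need not change, because the flag itself is left alone.
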